### ***Handling of missing data***

Missing data will be carefully evaluated, and reasons for missingness recorded wherever possible. Where appropriate, multiple imputation will be used, and analyses of imputed datasets will be presented alongside sensitivity analyses tailored to the type of missing data.

### ***Internal pilot***

This study will include an internal pilot phase, during which feasibility parameters will be assessed in an interim analysis of the first 100 participants, followed up to 6 months. Data from this phase will contribute to the definitive trial analysis. Pre-specified progression criteria will guide continuation: recruitment (“Go”  $\geq 75\%$  of target rate; “Amend” 50–74%; “Stop”  $< 50\%$ ), retention at the primary endpoint (“Go”  $\geq 90\%$ ; “Amend” 75–89%; “Stop”  $< 75\%$ ), intervention delivery fidelity (“Go”  $\geq 85\%$ ; “Amend” 60–84%; “Stop”  $< 60\%$ ), and completeness of primary outcome data (“Go”  $\geq 90\%$ ; “Amend” 70–89%; “Stop”  $< 70\%$ ). Safety signals or unexpected serious adverse events will prompt immediate review by the Trial Steering Committee. At the end of the internal pilot, the Trial Steering Committee will review feasibility data and determine whether to proceed without modification, continue with protocol amendments, or stop the trial.

### ***Motion analysis laboratory (MAL) evaluation***

A subset of 26 participants in the VELYS-assisted group and 26 participants in the manual group will undergo gold-standard 3D motion analysis (Vicon, Oxford, UK) to provide objective biomechanical (kinematic, kinetic and electromyographic) data which will be compared between groups and with a reference population of 52 age- and sex-matched healthy (native knee) controls using a 1:1:2 comparison ratio.

The primary outcome measure will be knee adduction moment (KAM), which is a validated biomechanical indicator of medial compartment loading, with elevated KAM values associated with increased medial knee contact forces and implant wear. Systematic review evidence demonstrates that manual TKA procedures consistently reduce peak KAM. However, not many studies have systematically evaluated KAM patterns following raTKA or compared these outcomes to healthy individuals, representing a significant gap in understanding the biomechanical benefits of this advanced surgical technique. Secondary outcomes will include:

- Spatiotemporal gait parameters (gait speed, step length);
- Kinematic parameters (knee range of motion in sagittal and frontal planes);
- Kinetic parameters, including peak hip flexion and adduction moments, peak knee flexion moment, knee adduction moment impulse, peak ankle dorsiflexion moment, and plantar loading symmetry;
- Joint power parameters, including hip, knee, and ankle power;
- Electromyographical assessment.

A sample size of 52 participants (26 in the raTKA and mTKA groups, respectively) has been determined to provide sufficient power to detect expected differences in medial knee contact force compared with matched healthy controls. The sample size calculation is based on peak knee adduction moment (KAM). Peak KAM for healthy controls is described as being  $0.46 \pm 0.13$  Nm/kg, and for prosthetic knees at six months after mTKA, it is  $0.61 \pm 0.13$  Nm/kg. Only one study has investigated peak KAM in patients who have undergone raTKA, demonstrating values of  $0.49 \pm 0.31$  Nm/kg at six months post-operatively. A power calculation was performed (SPSS Sample Power) and demonstrated that with an independent samples t-test, a sample of 26 subjects in each group (mTKA and raTKA) provided adequate power to detect a significant difference in peak KAM (large effect size [0.80],  $\alpha = 0.05$ ). Complementary MAL and technology-enabled assessments of real-world function, additional timepoints, and a larger sample may be added according to the availability of resources.

The motion analysis laboratory is based at the GJUNH, and subjects for the MAL study will be recruited from the GJUNH cohort of trial subjects. Patients will be invited to participate in the MAL study at the point of recruitment to the trial until the full sample (26 patients in each experimental arm) is complete. Recruitment to the MAL study will require separate informed consent due to the additional requirements for in-person attendance and testing pre-operatively and at 6 months post-operatively. Patients with a BMI of  $>40$  kg/m^2 will be excluded from the MAL study due to potential line-of-sight issues and greater soft tissue artefacts associated with anatomical placement of the retro-reflective markers and their subsequent movement relative to underlying bone during trials.

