### ***Sample size***

The sample size calculation is based on detecting a minimum clinically important difference (MCID) of 7 points in the FJS at six months post-operatively. This is informed by Alton et al (2025), and a standard deviation of 24 points, as reported in Clement et al., 2021. Using a one-sided alpha of 0.05 and a power of 80%, it was calculated that 147 participants per group would be required. To account for an anticipated 15% loss to follow-up, the final recruitment target is 173 participants per group, yielding a total study population of 346 participants.

Outcome data from the internal pilot (the first 100 study participants who have completed their 6-month follow-up) will be analysed. A blinded pooled estimate of the outcome variance will be computed and used in a pre-specified sample size re-estimation algorithm. The analysis team will remain blinded to treatment allocation; any sample size adjustments will be made according to the pre-specified rules to preserve type I error.

For the motion analysis sub-study, a sample size of 52 participants (26 in the raTKA and mTKA groups respectively) has been determined to provide sufficient power to detect expected differences in peak medial knee contact force compared with matched healthy controls.

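### The motion-laboratory sub-study says it is sized for comparison with healthy controls, but its only power calculation compares the two randomised arms

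*Protocol*

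**What the plan says.** The Protocol's section on the motion analysis laboratory (MAL) evaluation sets up three groups: 26 robot-assisted knees (raTKA), 26 manual knees (mTKA) and 52 healthy controls. The measurements will be "compared between groups and with a reference population of 52 age- and sex-matched healthy (native knee) controls using a 1:1:2 comparison ratio". For the outcome it states: "The primary outcome measure will be knee adduction moment (KAM").

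The purpose of the sample size is given twice. The main Sample size section says that 52 participants give "sufficient power to detect expected differences in peak medial knee contact force compared with matched healthy controls". The MAL section repeats this as "sufficient power to detect expected differences in medial knee contact force compared with matched healthy controls".

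The calculation in the MAL section is for another contrast, on peak KAM: "with an independent samples t-test, a sample of 26 subjects in each group (mTKA and raTKA) provided adequate power to detect a significant difference". It uses a "large effect size [0.80"] and alpha 0.05. Neither the sidedness nor a numerical power is stated.

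The same paragraph quotes peak KAM in Nm/kg: healthy 0.46 (SD 0.13), mTKA at six months 0.61 (SD 0.13), and raTKA at six months 0.49 (SD 0.31).

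**The concern.** The stated purpose and the calculation differ in two ways.

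- **Contrast.** The purpose sentences compare operated knees with healthy controls. The calculation compares the two operated arms.
- **Variable.** The purpose sentences refer to medial knee contact force. The calculation and the designated primary outcome use KAM, which the Protocol treats as an indicator of medial loading. Contact force is not among the sub-study's listed outcomes.

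This matters for interpretation. Only raTKA versus mTKA is protected by randomisation; the controls are an external reference group. A reader told that the sub-study is adequately powered against healthy controls may take a non-significant raTKA-versus-healthy test as evidence of normal loading. If mTKA versus healthy is significant at the same time, the pair is easily read as a benefit of the robot. That reading compares two significance verdicts and does not test the arms against each other.

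**Working it through.** **Inputs** (Protocol, MAL section): n = 26 raTKA, 26 mTKA, 52 controls; d = 0.80; alpha 0.05; means and SDs as quoted above. **Assumptions:** two-sided tests and normal data.

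**1. The Protocol's own figure.** For raTKA versus mTKA at d = 0.80, the noncentrality is 0.80 × √(26/2) = 2.88. The noncentral t gives 80.7% power, and 80% needs 25.5, so 26 per arm. The stated 26 is therefore the answer for the between-arm contrast, two-sided, at about 80% power.

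**2. Power against healthy controls on the quoted values.** This is not in the Protocol. SE = √(SD₁²/n₁ + SD₂²/n₂).

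- mTKA versus healthy: difference 0.61 − 0.46 = 0.15; SE = 0.13 × √(1/26 + 1/52) = 0.0312; ratio 4.80. In SD units 0.15/0.13 = 1.15. Power 99.7%.
- raTKA versus healthy: difference 0.49 − 0.46 = 0.03; SE = √(0.31²/26 + 0.13²/52) = √(0.003696 + 0.000325) = 0.0634; ratio 0.47. Simulated power is about 7% with Welch's test and about 17% with the pooled t-test.
- raTKA versus healthy with SD 0.13 in both groups: 0.03/0.13 = 0.23 SD; power about 16%.

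Power for raTKA against controls is thus low under either SD, mainly because the quoted means are only 0.03 apart.

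**3. How often the contrasts tell different stories.** Simulation of 26/26/52 at the quoted means, two-sided 5%, at least 100,000 trials per setting. The pattern counted is: mTKA versus healthy significant, raTKA versus healthy not.

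| SDs (mTKA, raTKA, healthy) | Test | Pattern | Pattern, with raTKA versus mTKA also not significant | Power, raTKA versus mTKA |
|---|---|---|---|---|
| 0.13, 0.31, 0.13 (quoted) | Welch | 92% | 51% | 42% |
| 0.13, 0.31, 0.13 (quoted) | pooled t | 83% | 42% | 43% |
| 0.13, 0.13, 0.13 | Welch | 84% | 5% | 90% |

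The fourth column depends heavily on the raTKA SD of 0.31. The third does not: even with equal SDs, a non-significant raTKA-versus-healthy test is the usual result.

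**The case against.** The strongest reply is that the intended contrast can be recovered. The MAL section names the test, the arms, the variable, the effect size and alpha, and 26 per arm reproduces for exactly that contrast. It mentions the between-group comparison first and calls the controls a reference population. On this view two sentences are loosely worded and nothing more. Most of this stands and sets the weight of the point. It does not remove the contradiction, because the main Sample size section gives only the healthy-control purpose, and a later analysis plan could not follow both statements.

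It can also be said that 26 against 52 has 90.8% power for a difference of 0.80 SD, so the sentence about controls would be true for an effect of that size. That is correct. However, the sentence speaks of expected differences, and the Protocol's quoted means put raTKA 0.03 Nm/kg from healthy.

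The 51% rests mainly on the raTKA SD of 0.31, which the Protocol takes from a single study. This objection stands, so the figure is given together with the 5%.

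Three stronger readings are tempting, and the document does not support them.

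- **Inflated family-wise error.** Three unadjusted 5% tests would give about 12% if all three means were equal. The Protocol does not say that three confirmatory tests will be run or that any one counts as success, and its own values put mTKA 1.15 SD above healthy. If that difference is real, at most one of the other two null hypotheses can be true, and the error is at most about 5%. Biomechanical outcomes are also listed as secondary, and the Multiple testing section declares secondary analyses exploratory and unadjusted.
- **Opposite answers.** The discordance is between significant and non-significant results on different contrasts. It is not a reversal in the direction of effect.
- **A flawed decision rule.** The Protocol nowhere says that the robot will be declared beneficial if manual differs from healthy and robot does not. That is a misreading to guard against, not a planned rule.

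**Conclusion.** The stated purpose of the sub-study's sample size contradicts the calculation offered in its support. The 26 per arm is justified for peak KAM between raTKA and mTKA at d = 0.80 (80.7% power, assuming a two-sided test). It was not derived for medial contact force, nor for comparison with healthy controls. On the quoted values the healthy-control claim holds for mTKA (99.7%) and fails for raTKA (about 7% by Welch, about 17% pooled). A non-significant raTKA-versus-healthy result would therefore say almost nothing about restored loading.

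These power figures assume that the quoted means and SDs are right and that the data are normal. The contradiction between the passages does not depend on them. The issue is minor: it concerns an exploratory nested sub-study and leaves the trial's primary conclusion untouched.

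**What to change.** Three edits to the Protocol, carried into the analysis plan:

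1. In the Sample size section and in the opening sentence of the MAL sample-size paragraph, replace the reference to contact force against healthy controls with peak KAM between raTKA and mTKA. State the sidedness and the power (80.7% if two-sided).
2. In the MAL section, name raTKA versus mTKA in peak KAM at six months as the sub-study's primary contrast.
3. Report both comparisons with healthy controls as mean differences with 95% confidence intervals. State that robot benefit will not be inferred from one significant and one non-significant comparison with controls.

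No participants, measurements or visits are added. The cost is that the healthy-control comparisons become descriptive and cannot carry a confirmatory claim.

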### ***Data collection***

Study data will be collected using a bespoke portal on REDCap (Research Electronic Data Capture, Vanderbilt University, USA) at predefined time points, aligned with the clinical care pathway. An option for in-person, postal, and telephone collection will also be available to participants at each time point. (Table 1)

At the pre-operative baseline visit, participants will complete the PROMs questionnaires (FJS, OKS, EQ-5D-5L, satisfaction scores, and pain score). Pre-operative bilateral hip-knee-ankle (HKA) radiographs will be obtained to assess coronal alignment, joint line obliquity, and enable CPAK classification. For participants enrolled in the motion analysis laboratory (MAL) sub-study, a baseline assessment will be conducted during the same hospital visit.

During surgery, data will be collected relating to surgical workflow and efficiency (including case time, tourniquet time, operating room preparation and turnaround times). For the raTKA group, VELYS-acquired intra-operative data will be collected. Data from inpatient medical records will be collected. Routine postoperative radiographs will be taken in line with standard clinical practice.

At six weeks post-operatively, participants will complete the PROMs questionnaires. In addition, participants will complete a health service resource use questionnaire, which will capture clinical service contacts (including frequency and reason) and analgesic use during the follow-up period.

At six months post-operatively, participants will complete the FJS (primary outcome), and secondary PROMs questionnaires, and post-operative bilateral HKA radiographs will be obtained to assess implant positioning and limb alignment. A further health service resource use questionnaire will also be completed. MAL sub-study participants will undergo a repeat assessment.

At 12 months post-operatively, participants will complete the full set of PROMs, along with a final health service resource use questionnaire.

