### ***Statistical analysis***

All analyses will adhere to CONSORT reporting standards. A detailed statistical analysis plan will be finalised with the Trial Steering Committee before any formal analyses are undertaken. Baseline characteristics will be summarised to assess comparability between treatment groups. Simple descriptive statistics will follow standard conventions, including means and standard deviations or medians and interquartile ranges as appropriate for continuous variables, and counts and percentages for categorical data.

The primary analysis will examine differences between the two intervention groups (using an intention-to-treat approach) with regard to their change in FJS (preoperatively versus 6 months post-surgery). A Student's independent t-test will be used to compare mean scores between groups. Assumptions of normality and equality of variances will be assessed using diagnostic plots and Levene's test. If variances are unequal, the Welch's t-test will be applied. The results will be reported as mean differences with 95% confidence intervals and p-values.

Secondary outcomes will be analysed similarly, appropriate to the type and distribution of the data. Categorical outcomes, such as patient satisfaction and complication rates, will be compared between groups using the chi-square test. If any expected cell count is less than five, Fisher's exact test will be applied. Effect sizes will be reported alongside these comparisons using risk ratios or odds ratios with 95% confidence intervals to provide a measure of the magnitude and precision of differences between groups.

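### The motion-laboratory sub-study is sized on an unadjusted t-test, and no analysis rule adjusts peak knee adduction moment for the pre-operative value measured in every participant

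*Protocol*

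**What the plan says.** The sub-study has its own primary outcome (Protocol, *Motion analysis laboratory (MAL) evaluation*): "The primary outcome measure will be knee adduction moment (KAM), which is a validated biomechanical indicator of medial compartment loading". The same section says the data will be compared between the arms and with healthy controls. It names no test, time point or covariate for that comparison.

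The sample-size paragraph of that section reports, for peak KAM: "with an independent samples t-test, a sample of 26 subjects in each group (mTKA and raTKA) provided adequate power to detect a significant difference in" this outcome, with a "large effect size [0.80"] and alpha 0.05. The values quoted in support are six-month ones for both operations.

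Pre-operative gait is measured in everyone in the sub-study. *Data collection* states: "For participants enrolled in the motion analysis laboratory (MAL) sub-study, a baseline assessment will be conducted during the same hospital visit". The MAL section bases its separate consent on the "additional requirements for in-person attendance and testing pre-operatively and at 6 months post-operatively", and Table 1 has a baseline MAL row.

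Biomechanical outcomes are listed among the trial's secondary outcomes (*Outcomes*). *Statistical analysis* gives the rule for these: "Secondary outcomes will be analysed similarly, appropriate to the type and distribution of the data". The analysis they are to resemble is an independent t-test on change in Forgotten Joint Score (FJS), or Welch's test if variances differ. The only covariate model in the protocol is under *Subgroup analyses*. It lists no baseline outcome value.

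**The concern.** A pre-operative measurement of the sub-study's own primary outcome will exist for every participant, yet neither the sizing nor the analysis rule uses it as a covariate. Where the pre- and post-operative values are correlated, adjustment removes part of the between-patient variance at almost no cost.

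The sub-study has little to spare. The recruitment target of 26 per arm equals the number the t-test requires, with no allowance for loss, although the main trial allows 15%. Randomisation is stratified by centre only and the sub-study has one centre, so nothing in the design balances pre-operative loading between two groups of 26. Knees with up to 15° of varus or valgus are eligible.

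At stake is the width of the interval on the trial's laboratory-based biomechanical comparison of the arms. It is also unclear whether the protocol means a six-month or a change comparison, and the two differ in power.

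**Working it through.** **Inputs.** From the MAL section: 26 per arm, standardised difference d = 0.80, alpha 0.05, six-month peak KAM 0.61 (SD 0.13) after manual and 0.49 (SD 0.31) after robot-assisted surgery. Not stated there: sidedness, the power figure (only called adequate) and r, the correlation between pre-operative and six-month peak KAM. Two-sided testing and 80% power are assumed because they reproduce the stated size. r is shown as a range.

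**Step 1, the plan's own figure.** For a two-sample t-test with n per arm, the noncentrality is d/√(2/n). With n = 26 this is 0.80/√(2/26) = 2.88 on 50 degrees of freedom. Power is 80.7%, and 26 is the smallest n that reaches 80%. A one-sided test would need 21, and 90% power would need 34 two-sided, so neither matches. The stated 26 per arm reproduces.

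**Step 2, the three candidate analyses at 26 per arm.**
- Six-month t-test: effective d = 0.80 whatever r is.
- Change-score t-test: the SD is multiplied by √(2(1 − r)), taking equal variances at both times. Effective d is 0.80/√1.4 = 0.68 at r = 0.3, 0.80/√1.0 = 0.80 at r = 0.5 and 0.80/√0.6 = 1.03 at r = 0.7.
- ANCOVA on pre-operative KAM: the residual SD is multiplied by √(1 − r²), with one degree of freedom lost. Effective d is 0.80/√0.91 = 0.84, 0.80/√0.75 = 0.92 and 0.80/√0.51 = 1.12.

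| Assumed r | Six-month t-test | Change-score t-test | ANCOVA | n per arm for 80% with ANCOVA |
|---|---|---|---|---|
| 0.3 | 80.7% | 66.7% | 84.2% | 24 |
| 0.5 | 80.7% | 80.7% | 90.4% | 20 |
| 0.7 | 80.7% | 95.5% | 97.7% | 14 |

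ANCOVA is ahead in every row. Below r = 0.5 the change score does worse than ignoring the baseline.

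**Step 3, with losses.** As an illustration, applying the main trial's 15% leaves 26 × 0.85 ≈ 22 per arm. Power is then 73.6% for the six-month t-test, and 77.5%, 84.9% and 95.2% for ANCOVA at r = 0.3, 0.5 and 0.7.

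**Step 4, at the quoted KAM values.** The implied d is 0.12/√((0.13² + 0.31²)/2) = 0.12/0.238 = 0.505, not 0.80. Power at 26 per arm is 43% for the six-month t-test. For ANCOVA it is 46%, 54% and 70% at r = 0.3, 0.5 and 0.7. Without adjustment, 63 per arm would be needed for 80%.

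**The case against.** The sentence naming the t-test reports a power calculation, and sizing on a t-test does not commit the analysis to one. This stands. A reader might infer that the protocol compares KAM by a six-month t-test from which pre-operative KAM is wholly absent, but the documents do not say so. The analysis method is reached only through the secondary-outcome rule, and the analysis that rule points to is on change, which uses the baseline by subtraction. The point therefore has to hold on both readings, and it does.

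A reader might also infer that chance imbalance in pre-operative loading biases the result. It does not: under randomisation the unadjusted interval already allows for such imbalance. The cost is precision.

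The size of the gain is open. Both operations change alignment deliberately, with different targets by arm, so a correlation of 0.5 cannot be presumed. This too stands, and the gain at 0.3 is small.

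It can further be said that covariates belong in the statistical analysis plan, or that adjusting the FJS analysis would carry over to KAM through the same rule. The first is only partly right: the protocol does name a default method, and a plan that followed it would be inefficient. The second is possible but depends on how the word for similarity is read, and it would not by itself name pre-operative KAM as the covariate.

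Finally, the protocol also describes the sample as sized for comparison with healthy controls. Adjustment of the randomised comparison does not address that contrast.

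**Conclusion.** The point holds as one of efficiency. The sub-study is sized on an unadjusted t-test, the only rule reaching its primary outcome is an unadjusted t-test on six-month values or on change, and no section adjusts for the pre-operative KAM it collects. At d = 0.80 and 26 per arm, ANCOVA adds about 3.5 points of power over the six-month t-test at r = 0.3, about 10 at 0.5 and 17 at 0.7. Over the change-score t-test it adds about 17.5, 10 and 2 points. These figures assume two-sided 5%, equal variances and complete data, and r is an assumption throughout.

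It is not a sizing error: 26 per arm is correct for the stated inputs. Nor should adjustment be taken as a cure for the separate mismatch between d = 0.80 and the quoted KAM values (d about 0.50). At those values power reaches only 70% at r = 0.7, and the mismatch needs its own answer.

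**What to change.** In *Motion analysis laboratory (MAL) evaluation*, state that the robot-assisted versus manual comparison is a linear model of six-month peak KAM on allocated arm and pre-operative peak KAM, with robust standard errors because the quoted SDs differ, reporting the adjusted mean difference with its 95% confidence interval. This also settles the time point and whether change or final value is compared. No centre term is needed because the sub-study is single-centre. The t-test can remain as the conservative basis for the sample size.

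The cost is one sentence and one degree of freedom, with no new visit, measurement or participant.

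### The motion-laboratory sub-study claims adequate power at an effect size of 0.80, but its quoted means and SDs imply about 0.50 and roughly 43% power, and the comparison it says it was sized for is not the one calculated

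*Protocol*

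**What the plan says.** The protocol describes the size of the sub-study in two places.

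- **Sample size.** The 52 participants are said "to provide sufficient power to detect expected differences in peak medial knee contact force compared with matched healthy controls".
- **Motion analysis laboratory (MAL) evaluation.** "The primary outcome measure will be knee adduction moment (KAM"). The opening of the sample-size paragraph repeats the healthy-control purpose, again in terms of medial contact force, and then says the calculation rests on peak KAM. It quotes peak KAM (Nm/kg) of 0.46 ± 0.13 in healthy controls and 0.61 ± 0.13 six months after manual TKA. For robot-assisted TKA it notes "Only one study has investigated peak KAM in patients who have undergone raTKA" and gives 0.49 ± 0.31 at six months. The calculation is a two-sample t-test between the manual and robot-assisted arms at alpha 0.05. The conclusion drawn is that 26 per arm "provided adequate power to detect a significant difference in peak KAM (large effect size [0.80"]).

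No power figure, sidedness or allowance for loss is given for the sub-study. The planned reference group is 52 healthy controls.

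**The concern.** There are two mismatches.

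First, the paragraph sets out literature values for the two arms being compared and then claims adequate power at an effect size those values do not produce. The robot-assisted SD is more than twice the manual SD, which pulls the standardised difference well below 0.80.

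Second, the stated purpose (contact force, against healthy controls) differs from the calculation shown (peak KAM, manual against robot-assisted) in both endpoint and comparator.

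What is at stake is how the sub-study will be read. If the quoted values are about right, the design has less than an even chance of detecting the between-arm difference that they imply. A non-significant result published alongside a claim of adequate power could then be taken as evidence that the arms do not differ. A claim of power against healthy controls would likewise invite a reader to interpret a null robot-assisted result as normal loading.

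**Working it through.** **Inputs, all from the MAL evaluation section unless stated.** 26 per arm; 52 healthy controls; alpha 0.05; assumed effect 0.80; peak KAM 0.61 (SD 0.13) manual, 0.49 (SD 0.31) robot-assisted, 0.46 (SD 0.13) healthy. The 15% loss comes from the main trial's Sample size section. Assumptions: a two-sided test and an 80% target, because neither is stated.

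**1. Reproducing the plan's figure.** With d = 0.80, two-sided 5% and 80% power, the noncentral-t calculation gives 25.5, so 26 per arm. Power at 26 is 80.7%. A one-sided 5% test would need only about 20 to 21 per arm, so 26 fits a two-sided test.

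**2. Effect size from the quoted values.**
- Difference: 0.61 − 0.49 = 0.12.
- Pooled SD: √[(0.13² + 0.31²)/2] = √[(0.0169 + 0.0961)/2] = √0.0565 = 0.238.
- d = 0.12/0.238 = 0.505.

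**3. Power at 26 per arm with d = 0.505.** The noncentral t gives 43.1%. Simulation with the unequal SDs gives 43.3% (Student) and 42.4% (Welch). A one-sided 5% test would give 56%. Reaching 80% two-sided would take 63 per arm.

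**4. What 0.80 requires.** Common SD = 0.12/0.80 = 0.15. Alternatively, keeping the manual SD at 0.13, the robot-assisted SD would be √(2 × 0.15² − 0.13²) = √0.0281 = 0.168, a little over half the quoted 0.31.

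**5. Sensitivity to the SD (difference 0.12, 26 per arm, two-sided 5%).**

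| SD assumed | d | Power |
|---|---|---|
| 0.13 in both arms | 0.92 | 90% |
| 0.15 in both arms | 0.80 | 81% |
| 0.13 and 0.31 as quoted | 0.505 | 43% |
| 0.31 in both arms | 0.39 | 28% |

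**6. Detectable difference.** At 26 per arm and 80% power the smallest detectable d is 0.792. At the quoted SDs that is 0.792 × 0.238 = 0.19 Nm/kg, against 0.12 quoted. It is 0.792 × 0.13 = 0.10 at SD 0.13 and 0.792 × 0.31 = 0.25 at SD 0.31.

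**7. Loss.** With 15% loss, 26 × 0.85 ≈ 22 per arm. Power is 74% at d = 0.80 and 37% at d = 0.505.

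**8. Against 52 healthy controls, on KAM.**
- Manual: (0.61 − 0.46)/0.13 = 1.15; power over 99%.
- Robot-assisted: difference 0.49 − 0.46 = 0.03; SE = √(0.31²/26 + 0.13²/52) = 0.063. Power is about 7% by Welch simulation and 9% by the pooled noncentral t, so about 8%.

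**9. Adjusting for pre-operative KAM.** Residual SD = SD × √(1 − ρ²), so d becomes 0.505/√(1 − ρ²). At ρ = 0.5, d = 0.58 and power is 54%. At ρ = 0.7, d = 0.71 and power is 71%. These correlations are assumed; the protocol gives none.

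**The case against.** The strongest reply is that nothing was miscalculated. The protocol states n, test, effect size and alpha, and these reproduce. It labels 0.80 as large, which reads as a conventional target, and never says 0.80 was derived from the quoted means or that 0.12 is the expected difference. This stands: a reader might infer an arithmetic error, and the document does not support that. What remains is that the paragraph presents peak KAM values as the basis of the calculation, then uses an effect size that they do not yield, without explanation.

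A second reply is that 43% leans on one SD from one study, set against a manual value from other sources. This also stands, and it is why the table gives a range from 28% to 90%. It does not rescue 0.80, because 0.31 is the only robot-assisted SD quoted and no reason is given for setting it aside.

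Third, a reader might infer that the healthy-control claim is simply false, or that the comparison was never sized. The document supports only that no calculation is shown. On the quoted KAM values the claim is sound for manual knees. The low robot-assisted figure reflects a quoted difference of only 0.03. The contact-force wording is largely loose phrasing, since KAM is introduced as an indicator of medial loading and the next sentence names it as the basis.

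Finally, the sub-study serves a secondary objective, and the Multiple testing section treats secondary analyses as exploratory, reported with confidence intervals. That lowers the stakes but does not make the power statement correct. The possible larger sample depends on resources and is not a commitment.

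**Conclusion.** The statement that 26 per arm "provided adequate power to detect a significant difference in peak KAM" is not supported by the values quoted beside it. On those values power is about 43%, or about 37% with 15% loss. Across the quoted SDs it runs from 28% to 90%, and 0.80 corresponds to none of them. The stated purpose also names an endpoint and comparator for which no calculation is shown; on KAM it holds for manual knees and not for robot-assisted knees.

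These figures assume a two-sided 5% test, approximately normal data and the quoted cross-study means and SDs. The 43% should be read as what the protocol's own inputs imply, not as the true power. The point concerns the sub-study only: the Forgotten Joint Score analysis and the target of 346 are untouched. It should be corrected, but it does not threaten the main trial.

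**What to change.** 1. In both the Sample size and MAL evaluation sections, name what was sized: peak KAM at six months, robot-assisted against manual TKA.
2. Replace the claim of adequate power with the difference detectable at 80% power (about 0.19 Nm/kg at the quoted SDs, beside the 0.12 quoted). Alternatively, state the power as about 43% with its range over the SD. Either way, give the sidedness and the effect of loss. If 0.80 is kept, say why the SD of 0.31 is set aside.
3. Limit any statement of power against healthy controls to manual TKA on KAM. Present robot-assisted against healthy as an estimate with a confidence interval.
4. Analyse six-month KAM adjusted for the pre-operative KAM, since Table 1 already schedules a baseline laboratory visit. If the baseline correlation is 0.5 to 0.7, power at the quoted values rises to about 54% to 71%, still short of 80%.

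The cost is a change of wording, one covariate and a less favourable stated power. No additional patients or visits are needed.
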